2.2.4 Subject Withdrawal Criteria

Subject participation is strictly voluntary, and a subject may withdraw from the research study at any time. Subjects may withdraw or take away permission to use and disclose health information at any time by sending written notice to the study doctor. If a subject withdraws permission, the subject will not be able to continue being in the research study. When permission has been withdrawn, no new health information will be gathered after that date. Information that has already been gathered may still be used and given to Sponsor.

The Investigator/Sponsor may recommend dropping a subject from the study at any time. Recommendations to drop a subject may include but are not limited to: misuse of study product, not following study procedures, or a serious protocol violation.

Subjects that withdraw or drop from the research study will not be replaced.

If, for any reason, a subject does not complete the study, an explanation will be entered on the Subject Accountability CRF. All data gathered on the subject prior to discontinuation will be made available to the Sponsor.

3. TREATMENTS

3.1.1 Product Usage

Washout Product:

Subjects will be instructed to brush twice daily (morning and at bedtime) with their washout toothpaste and toothbrush following the brushing instructions found in the Appendix.

Treatment Product:

Subjects will be instructed to brush twice daily (morning and at bedtime) with their assigned dentifrice for 21 days following the brushing instructions found in the Appendix. Subjects will be instructed to brush the biting surfaces of their back teeth (but not enamel specimens) with a full ribbon of study dentifrice for one timed minute while wearing their partial dentures, followed by rinsing with the 15 mL of measured tap water for 10 seconds and then expectorating. Subjects who are regular floss users will be allowed

to continue flossing; use of any non-study related products will be disallowed. Compliance with brushing procedures will be recorded in subject diaries (see Appendix), as well as any *de novo* or changes in medical conditions, medications or treatments.

3.1.2 Method of Assigning Subjects to Treatment Groups

Study Design	n	Number of Treatment Periods	Treatment Sequences
Crossover	16	4	ABCD, BDAC, CADB, DCBA

Treatment Sequence Schedule

Eligible subjects will be randomly assigned to one of the 4 pre-specified treatment sequences. Subjects will be assigned to a treatment sequence in the order they come to the site for their first treatment period using a computer-generated treatment sequence schedule. The site will keep the treatment sequence schedule while the study is on-going. Subjects will complete the treatment sequence in the order assigned to them. Should a subject miss a treatment period, that treatment in the sequence will be skipped.

Period 5: The crossover design does not apply to Period 5. All subjects will receive the same product in Period 5.

3.1.3 Prior and Concomitant Therapy

Medical history and concomitant medication will be recorded as source documentation.

3.1.4 Treatment Compliance

Product use compliance will be assessed by determining the average weight of each type of test product prior to dispensing (five tubes per product will be weighed and average weight determined). At the end of each treatment period, subjects will be required to return all product containers (including empty ones) to the study site. The tubes will be individually weighed upon return and that number subtracted from the average weight will be recorded on the treatment dispensing log.

The amount of test product used for each study treatment will be compared to daily product usage recorded on the subject's diary. Significant discrepancies will be discussed with the study subject, as needed. Subjects who miss 15% or more treatments within the three-week treatment period will be considered non-compliant. The reason for non-compliance will be noted in the subjects' study records. All subjects will be instructed to use only the assigned products in place of normal oral hygiene for the duration of the study.

3.2 Assessment of Efficacy

3.2.1 Sample Collection

Salivary Flow Assessment

Salivary flow will be assessed during the screening visit. For the unstimulated collection, subjects will sit quietly for five minutes before beginning the test. During the five-minute test time, they will be told to allow their saliva to pool, emptying into a collection cup whenever they feel the need to swallow.

For the stimulated collections, subjects will chew unflavored gum base for one minute and then swallow any pooled saliva. They will then chew the gum base for two minutes, during which time they will empty any pooled saliva into a collection cup.

The samples will be weighed and the salivary flow rates determined. The unstimulated saliva flow rate must be ≥ 0.2 mL/min and the stimulated saliva flow rate must be ≥ 0.8 mL/min for study qualification.

Diary for Home Use

At the start of each treatment period, subjects will be provided with a diary (see Appendix) to record the date, and the time of the morning (a.m.) and evening (p.m.) of each brushing and any deviation from the brushing regimen. In addition, subjects will also record any new or changes in pre-existing medical conditions, medications or non-drug treatments or any change in signs or symptoms that may occur.

Subjects will be required to bring the completed diary to the end of treatment visit. Study staff will review the Diary with the subject to confirm treatment compliance and clarify listed medical conditions, medications and non-drug treatments.

Intra-oral Appliance

The in-situ model involves the placement of gauze-covered enamel specimens in the subject's mandibular partial denture (see Figure 1). The subject's denture will be prepared for the study by creating two hollows in the buccal flange area on one side of the partial denture and in two denture teeth on the same side large enough to accommodate the enamel specimens. Four gauze-covered 4 mm round enamel specimens will be mounted on the partial denture as described previously. The enamel specimens will be mounted in place with DentuSil™ - Silicone Soft Reline Material (The Harry J. Bosworth® Company, Skokie, IL) or an equivalent material. The DentuSil™ material will be placed in the drilled sites and the enamel specimens carefully inserted so that they be mounted flush with the surface of the buccal flange/denture teeth when fully seated. Great care will be taken to avoid contaminating the enamel surface of the specimens with the luting material. Upon completion of the study the subject's partial denture will be repaired. The location where the enamel specimens will be placed on the subject's partial denture are not functional parts of the denture, and the experimental procedures will not cause any permanent damage to the denture.

Prior to placement in the subjects' partial dentures, all enamel specimens will be sterilized by exposure to ethylene oxide.

FIGURE 1

Lower Partial Denture Appliance with specimens placed in the buccal flange and buccal surface of posterior denture teeth

3.3 Assessment of Safety

3.3.1 Safety Variables

Oral Examination

The study dentist will complete an oral soft and hard tissue (OSHT) examination at screening, oral hard tissue (OHT) at Visit 2 and 21 (and Visit 26 for those subjects participating in Period 5) and an oral soft tissue (OST) examination at each study visit with the exception of the 7-day and 14-day removal visits.

The exams will be conducted via a visual examination of the oral cavity and perioral area utilizing a standard dental light, dental mirror, gauze, and periodontal probe and tongue blade, as needed. The soft tissue structures examined will involve the labial mucosa including lips, buccal mucosa, mucogingival folds, gingival mucosa, hard and soft palate, tonsillar and pharyngeal areas, Edentulous ridge/Retromolar area, tongue, sublingual area/floor of mouth, submandibular area, major salivary glands, head and neck and TMJ. Observations will be listed as "Normal" and "Abnormal" and abnormalities will be described.

The hard tissue structures examined will include assessing for enamel irregularities, tooth fracture, pathologic tooth wear, cavitated lesions, active non-cavitated lesions, residual roots, faulty restorations and implants. Observations will be listed as "Absent" or "Present" and conditions noted as present will be described.

All abnormal findings are recorded and categorized by their location with hard tissue findings categorized as "other-oral." An AE is recorded if a new abnormal finding is noted after treatment application or any abnormal finding noted prior to treatment application increases in severity after treatment is applied.

3.3.2 Adverse Event Management

An adverse event (AE) is any untoward medical occurrence in a subject administered a product and which does not necessarily have a causal relationship with this treatment. An AE can therefore be any unfavorable and unintended sign (including an abnormal laboratory finding), symptom or disease temporally associated with the use of a medicinal (investigational) product, whether or not related to the medicinal (investigational) product.

A serious adverse event (SAE) is defined as an event which suggests a definite hazard or handicap to the subjects. SAEs are any events resulting in death, life threatening situation, disability or permanent damage, hospitalization or prolongation of existing hospitalization, or congenital anomaly/birth defects; events requiring intervention to prevent permanent impairment/damage; or other serious (important) medical events.

All other AEs that do not fit within these criteria will be considered "non-serious." Unexpected adverse event/reaction is any occurrence the nature or severity of which is not consistent with the AE provided in the current summary of product characteristics. All other AEs are considered "expected."

When an AE is suspected, all relevant evaluations will be carried out and appropriate treatment will be recommended. Additional follow-up will be performed as necessary and recorded as source documentation, with the results provided to the Sponsor. Subjects that experience any clinically significant AE will remain under medical supervision until the Principal Investigator/Medical Monitor recommends appropriate follow-up treatment or deems the AE to be resolved, stabilized, or no longer serious enough to warrant follow-up.

When an Investigator is notified of a serious AE, the Investigator must promptly (within 24 hours) notify the Sponsor (Clinical Trial Manager or the Medical Monitor) of the serious event, regardless of causality. Within 5 working days, a written and/or electronic report describing the circumstances of the event must be submitted to the Sponsor. The Investigator will be responsible for SAE reporting to the IRB.

3.3.3 Adverse Event Reporting

AE Recording

When an AE occurs after written informed consent has been obtained but before the first dose of study drug, the AE will be considered a nontreatment-emergent AE. Only serious nontreatment-emergent AEs related to study procedures will be recorded on the CRF. All nontreatment-emergent AEs that are non-serious or unrelated to study procedures should be documented by updating the medical history and general comments as applicable.

An AE that occurs from the time the subject receives the first dose of study drug until dismissed from the study will be considered a treatment-emergent AE. All treatment-emergent AEs will be collected. The severity, action taken, causality, outcome, and category of all recorded AEs will be recorded.

Severity

Severity refers to the extent to which an AE affects daily activities. Severity will be categorized according to the following criteria:

- Mild: Normal activities unaltered;
- Moderate: Normal activities altered;
- Severe: Unable to undertake normal activities.

The term “severity” is not the same as “serious.” Seriousness, not severity, serves as the guide for defining regulatory reporting obligations.

Action Taken

If any action was taken due to the AE, it should be recorded.

- None: No action was taken by the subject.
- Discontinued: Investigator recommended, or subject stopped using the study products.
- Reduced/Interrupted: Investigator recommended or subject reduced or interrupted the instructed product usage.

Causality

Causality refers to the relationship of the AE to study drug. Assessment of causality is the responsibility of the Principal Investigator at each site. If this responsibility is delegated to a sub-investigator, this should be appropriately documented in the delegation sheet. Causality will be categorized according to the following criteria:

- Doubtful: There is no medical evidence to suggest that the AE may be related to study drug usage, or there is another more probable medical explanation.
- Possible: There is medical evidence to suggest that the AE may be related to study drug usage. However, other medical explanations cannot be excluded as a possible cause.
- Probable: There is strong medical evidence to suggest that the AE is related to study drug usage.
- Not Related: There is no evidence to suggest the adverse event is related to study drug usage.

Category

Category refers to the region or area where the AE occurred. Categories are listed 0-9.

- 0 = Non-oral related
- 1 = Perioral area/lips
- 2 = Labial mucosa/buccal mucosa
- 3 = Mucolabial fold/mucobuccal fold
- 4 = Gingiva/free and attached
- 5 = Palate/hard and soft
- 6 = Oropharynx/uvula
- 7 = Tongue
- 8 = Sublingual
- 9 = Other oral

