2.1.5 Duration of Subject Participation

Visit 1 (Screening)

Subjects who have been recruited for the study via a telephone interview will sign in at the study site for this and all subsequent visits. At this time, subjects will be asked to read and sign duplicate copies of an informed consent statement, authorization for the release of health information for research form and demographic form. Demographic information and study entry criteria will be obtained and documented on the appropriate case report form (CRF). Upon review of these documents, an update of their medical

history/medications and the inclusion/exclusion criteria, each subject will be given an oral soft/hard tissue exam (OSHT) prior to their acceptance into the study. Their mandibular partial denture will be examined to determine if specimens can be held in one buccal flange area and the posterior denture teeth of the same side, as previously described. They will then provide a stimulated and unstimulated saliva sample to determine salivary flow rate. If no contraindications to their participation are discovered and the subject meets the study requirements, the subject will be accepted into the study.

General comments, if any, will be recorded on the appropriate CRF.

Visit 2 (Prophy Period 1)

Two to three days prior to the beginning of Treatment Period 1, subjects will return for a professional dental prophylaxis. Subjects will answer have their medical history/medication information updated and answer continuation questions. Subjects will then receive an oral soft tissue exam (OST) and oral hard tissue exam (at the first period only). The subject's mandibular partial denture will be prepared to hold the round enamel specimens by drilling out hollows in the partial dentures at the specimen sites in the buccal flange area and the buccal surface of two denture teeth on the same side of the partial denture. A temporary dental material (DentuSil™) will be placed in the drilled-out areas of the partial denture. Subjects will be given fluoride-free toothpaste to use at home for the next two to three days until they return for their next visit. They will be encouraged to remove their partial denture at night until their next visit.

Visit 3 (Begin Treatment Period 1)

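### The AE form cannot attribute harm to study procedures or the appliance, and non-serious procedure-related events before first dose are recorded outside the AE CRF

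*Combined protocol and SAP*

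**What the plan says.** Section 3.3.3 sets the causality question: "Causality refers to the relationship of the AE to study drug". The codes are *Doubtful*, *Possible*, *Probable* and *Not Related*, and each is worded in terms of study drug usage. Two of them read:

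- "Doubtful: There is no medical evidence to suggest that the AE may be related to study drug usage", with the alternative "or there is another more probable medical explanation";
- "Not Related: There is no evidence to suggest the adverse event is related to study drug usage".

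For events after consent but before the first dose, the same section says: "Only serious nontreatment-emergent AEs related to study procedures will be recorded on the CRF". The rest are handled as follows: "All nontreatment-emergent AEs that are non-serious or unrelated to study procedures should be documented by updating the medical history and general comments as applicable". From first dose until dismissal, every AE is collected with severity, action taken, causality, outcome and category.

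Under 2.1.5 the denture is prepared at Visit 2 by "drilling out hollows in the partial dentures at the specimen sites", and a temporary material is placed in the hollows. Randomized product is issued at Visit 3, 2 to 3 days later. Section 3.3.1 makes an abnormal finding an AE if it is new after treatment application, or if it was present before and then becomes more severe. The safety analysis in 5.1 is a listing of reported AEs. Table 1 marks the Adverse Events row for the whole column that holds Visits 2, 7, 12, 17 and 22.

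**The concern.** Much of what subjects undergo in this trial is procedure rather than toothpaste: a drilled and relined denture, gauze-covered enamel mounted in it, round-the-clock wear for 21 days, a prophylaxis before each period and repeated specimen removal. A mucosal sore under the altered denture is a natural event to expect. The form has no place to say that the appliance caused it.

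The plan does use relatedness to study procedures as a filter before first dose, but gives no scale for it and does not carry it into the period after first dose. The earliest days with an altered denture also follow a different recording rule from the corresponding days of later periods. A reader of the listing could not pick out appliance-related events, and would not expect to find the non-serious ones from the first lead-in.

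**Working it through.** The plan states no figure on this point. The check sets the recording rules against the visit schedule; the only arithmetic is the length of the window.

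**1. Can any AE field carry attribution to a procedure?** The fields in 3.3.3 are severity (effect on daily activities), action taken (whether product use was stopped, reduced or interrupted), causality (study drug only), outcome and category (anatomical region, 0 to 9). None of those the section defines asks about the procedure or appliance. A buccal sore from the denture would be recorded by site, severity and relation to toothpaste, and no more.

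**2. The same non-serious, procedure-related event in two lead-ins.**

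| | Lead-in to Period 1 (Visit 2 to first dose) | Lead-in to Periods 2 to 5 |
|---|---|---|
| Procedures | Prophylaxis, first drilling, filling of hollows | Prophylaxis; Visit 2 to 6 procedures repeated |
| Status in 3.3.3 | Before first dose, so not treatment-emergent | After first dose, so treatment-emergent |
| Where recorded | Medical history (source documentation, 3.1.3) and general comments (a CRF, but not the AE CRF, 2.1.5) | AE CRF |
| Finding at an oral exam (3.3.1) | AE only if it becomes more severe after treatment | AE if new |
| In the 5.1 listing | Not expected | Yes |
| Table 1, Adverse Events row | Marked | Marked |

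One Table 1 entry therefore works under two recording rules.

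**3. Size of the window.** Inputs: lead-in 2 to 3 days, treatment 21 days, washout 4 to 5 days (2.1.2), four crossover periods, three washouts between them.

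- Visit 2 to Visit 21, shortest: 4 × (2 + 21) + 3 × 4 = 92 + 12 = 104 days.
- Visit 2 to Visit 21, longest: 4 × (3 + 21) + 3 × 5 = 96 + 15 = 111 days.
- Share before first dose: 2/104 = 1.9% to 3/111 = 2.7%, so about 2 to 3%.

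All 16 planned subjects pass through it. It is one of four lead-ins, or one of five for those who take Period 5.

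**4. Do the codes separate?** *Doubtful* has two limbs: no medical evidence of a relation, or a more probable alternative. *Not Related* is "There is no evidence to suggest the adverse event is related to study drug usage". An event with no evidence of a drug relation meets the first limb of *Doubtful* and also *Not Related*. The choice is left to the assessor.

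**The case against.** The strongest reply is that little is lost.

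- **Before first dose.** Non-serious events must be documented. General comments are on a CRF, and abnormal findings at the Visit 3 soft-tissue exam are recorded and described under 3.3.1. Serious procedure-related events do go on the CRF, and 3.3.2 sends SAEs to the sponsor whatever their cause.
- **After first dose.** Nothing is filtered by cause. A denture sore coded *Doubtful* is a correct answer to the question asked, and *Possible* remains available if the toothpaste cannot be excluded.
- **The window.** It is short, no specimens are mounted during it, the hollows are filled, and subjects are encouraged to take the denture out at night. Section 3.2.1 says the specimen sites are not functional parts of the denture.
- **The two rules.** Using a procedure filter before any drug exposure is not in itself a contradiction.
- **The codes.** Section 5.1 plans no tabulation or test by causality, so their overlap does not change which events are listed.

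All of this stands. It rules out two stronger readings that a reader might infer. One is that procedural harm goes unreported or is wrongly coded as unrelated; the documents show that it is recorded, and that the drug-causality code can be right as far as it goes. The other is that the trial fails to establish the safety of the in-situ model; its stated purposes in 2.1 are fluoride dose response and the model's performance with SnF₂, and 6.2 separately requires an investigator report covering adverse events. What the reply does not answer is that the AE listing carries no attribution to the appliance and treats the first lead-in differently from the others.

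**Conclusion.** The point holds as a minor one. After first dose, events are kept but their attribution to procedure or appliance is not. Before first dose, non-serious procedure-related events in a window of 2 to 3 days are documented elsewhere and would be expected to be missing from the AE listing. Separately, two of the four causality codes can fit the same event.

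This rests on three assumptions. First, that the 5.1 listing is drawn from the AE CRF, which the text implies but does not state. Second, that first dose means the randomized product issued at Visit 3; the fluoride-free paste given at Visit 2 is not among the investigational products in 1.2. Third, nothing is assumed about frequency: the documents give no AE rates, so the number of events affected is unknown. Whether specimens are mounted before or after first dose at Visit 3 is also not stated; if before, that step too falls in the window. No efficacy endpoint, comparison or conclusion changes.

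**What to change.** In 3.3.3 and on the AE CRF:

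- **(a)** Add an item for relationship to study procedures or appliance, alongside the study-drug item.
- **(b)** Record procedure-related AEs on the AE CRF from Visit 2 onward, serious or not, flagging those before first dose. Reconcile this with the rule in 3.3.1 for findings present before treatment and with the Adverse Events row of Table 1.
- **(c)** Limit *Doubtful* to its second limb, a more probable alternative explanation, and keep absence of evidence for *Not Related*.

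In 5.1, show both causality items in the AE listing.

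The cost is one CRF field, a few edited sentences and a slightly longer listing with some more minor events. Treatment, visits, endpoints and sample size are untouched.
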